# 1. Summary

Title of the study:				
Phase I clinical study, to evaluate the safety and tolerability of the preservative-free ophthalmic solution PRO-087 versus Xyel Ofteno ® and Systane Ultra ® , on the ocular surface of ophthalmological and clinically healthy subjects.				
Protocol code:		Creation date:		
SOPH087-0616/I		29/06/2016		
Protocol version:		Date of the version:		
1.0		29/06/2016		
Therapeutic Indication:				
Eye lubricant				
Study period:	Davalanman			
3 to 4 months	Development	t phase: I		
Goals:				
To evaluate the safety and to manufactured by Sophia Laborato subjects.	lerability of ries, S.A. of	the preservative-free formulation PRO-087 C.V. on the ocular surface of clinically healthy		
Hypothesis:				
To evaluate the safety and tolerability of the preservative-free formulation PRO-087 manufactured by Sophia Laboratories, S.A. of C.V. on the ocular surface of clinically healthy subjects.				
Methodology:				
Phase I clinical trial, controlled, of parallel groups, double blind, randomized, exploratory.				
Number of patients:				
30 subjects, divided into 3 groups [2	10 subjects (2	0 eyes) exposed by group]		
Diagnosis and main inclusion criter	ria:			
Systemically and ophthalmologically healthy subjects - Signed informed consent. - Age between 18 to 40 years. -Both genders - Blood tests [complete blood count (BHC), three element blood chemistry (QS) and liver function tests (PFH)] within normal parameters - Visual capacity 20/30 or better				

#### Test product, dose and route of administration, lot number:

- PRO-087. Chondroitin sulfate 0.18% / 0.1% sodium hyaluronate, ophthalmic solution free of preservatives. Prepared by Sophia Laboratories, S.A. of C.V., Zapopan, Jalisco, Mexico.
  - Dosage: 1 drop 4 times a day during the waking period, both eyes
  - Route of administration: topical ophthalmic

#### Duration of treatment: 10 days

#### Reference product, dose and route of administration, lot:

- 1. **Xyel Ofteno**®. Xantana gum 0.09% / Chondroitin sulfate 0.1% / preservative-free ophthalmic solution. Prepared by Sophia Laboratories, S.A. of C.V., Zapopan, Jalisco, Mexico.
  - a. Dosage: 1 drop 4 times a day during the waking period, both eyes
  - b. Route of administration: topical ophthalmic
- 2. **Systane Ultra®.** Polyethylene glycol 400 0.4%, propylene glycol 0.3%. Prepared by Alcon Laboratories, Inc.
  - a. Dosage: 1 drop 4 times a day during the waking period, both eyes
  - b. Route of administration: topical ophthalmic

#### Evaluation criteria:

#### Primary security outcome variables:

- Density of goblet cells.
- Presence of adverse events.
- Intraocular pressure.
- Visual ability
- Laboratory tests: BHc, QS and PFH.
- Epithelial defects in cornea and conjunctiva.
- Ophthalmological signs: conjunctival hyperemia, chemosis.

#### Secondary outcome variables:

- Rupture time of the tear film
- Life signs: FC, FR, TAS.
- Subsequent segment

#### Primary outcome variables of tolerability:

- Burning
- Foreign body sensation
- Itching
- Eye comfort index

#### Statistical methodology:

The data will be expressed with measures of central tendency: mean and standard deviation for the quantitative variables. The qualitative variables will be presented in frequencies and percentages. The statistical analysis will be carried out through the Kruskal-Wallis test for quantitative variables. The difference between the qualitative variables will be analyzed by means of X2 (Chi2). An alpha  $\leq$  0.05 will be considered significant.

# 3. Index of abbreviations

ALT	Alanino transferase
AST	Aspartate transferase
BAK BD BI	Benzalkonium chloride Bilirubin direct Bilirubin indirect
ВНс	Complete blood count
BPC BT	Good clinical practices Total Bilirubin
CV	Visual capacity
ССІ	informed consent letter
CIC	Cytology by conjunctival impression
IEC	Research Ethics Committee
CI	Informed Consent
CRF	Case Report Form (Case Report Form)
EA / EAS	Adverse event / serious adverse event
FDA	Food and Drug Administration (Food and Drug Administration)
FC	Heart rate
FR	Respiratory frequency
GAG	Glycosaminoglycans
ІСН	International Conference on Harmonization
ICO	Eye comfort index
IP	Principal investigator of the clinical study
PFH	Liver function tests
IOP	intraocular pressure
TAS	Systemic blood pressure

TF	Fluorescein stainin
TF	Fluorescein stainin

TVL	Green lysine stain
-----	--------------------

- QS Blood chemistry
- TVL Green lysine stain
- QS Blood chemistry

# Page left intentionally blank

# 5. Introduction

# 5.1 Theoretical framework

Dry eye disease (DED) is a frequent ocular condition that significantly decreases quality of life and affects 6-34% of the world's adult population. [1] [2] Although there is no formal study on the prevalence of the disease in Latin American countries, several reports agree that there is a higher prevalence of severe symptoms and clinical diagnosis of DED in the Hispanic population when compared with the Caucasian population. [2] [3]

DED is an alteration of the tear film that results in damage to the ocular surface and is associated with symptoms of ocular discomfort. The DED has also been called keratoconjunctivitis sicca (KCS), sicca syndrome, xerophtalmia, dry eye syndrome, ocular surface disease, tear film dysfunction syndrome (SDPL) or simply dry eye. [4] [5] Strictly some of these terms are not synonymous, since for example, the DED can be presented without keratitis, KCS; This protocol will be used as a synonym of the DED to the SDPL, assuming they are interchangeable concepts and adopting the definition of the International Dry Eye Seminar 2007 (DEWS, for its acronym in English of International Dry Eye Workshop):

Multifactorial disease of the tear and the ocular surface that results in symptoms of discomfort, visual alterations and instability of the tear film with potential damage to the ocular surface. It is accompanied by an increase in the osmolarity of the tear film and inflammation of the ocular surface. [4]

The SDPL is an alteration of the functional lacrimal unit (ULF), an integral system comprised of lacrimal glands, ocular surface (cornea, conjunctiva and Meibomian glands), eyelids and the sensory motor nerves that interconnect them. [6]

This ULF controls the main components of the tear film and regulates them in response to environmental, endocrinological and cortical influences. Its main function is to preserve the integrity of the tear film, the transparency of the cornea and the quality of the image projected onto the retina. [6] [7] [8] [9]

The damage or alteration to any component of the ULF can destabilize the tear film and lead to an eye surface disease that is expressed as SDPL. The stability of the tear film, distinctive of a normal eye, is threatened when the interactions between the stabilizing constituents of the tear film are compromised by decreased secretion, delayed clearance and an altered tear composition. Inflammation is a secondary consequence. The reflex tear secretion, in response to irritation, is considered to be the initial compensatory mechanism, but, over time, the inflammation that accompanies secretory dysfunction and decreased corneal sensitivity compromises the reflex response and results in instability of the even bigger tear film. It is considered that the disturbance of the UFL plays a very important role in the evolution of different forms of dry eye. [4]

The tear film is a highly specialized and carefully structured moisturizing layer that covers the cornea and the conjunctiva. It is classically described as a trilaminar structure composed of a lipid surface layer, an aqueous intermediate layer and a mucinous inner layer. [10] The tear film has four main functions: 1) Maintain a regular optical surface, 2) Do not allow friction between structures of the ocular surface, 3) Nourish the cornea and 4) First line of defense against ocular surface infections.[11]

CONFIDENTIAL

Based on the models of the "microstructure" of the tear film and its interface with the cells of the ocular surface, the mucin layer should always be present in a healthy tear film. [10] This layer provides support to the rest of the tear film on the ocular surface, helping to keep it moisturized and lubricated. [12] The epithelial cell layer of the conjunctiva includes the goblet cells, which are mucin excretors. The main source of mucin for the tear film are these cells. [11]

Within the framework of the DEWS, the etiopathogenic classification of the SDPL was established, which is summarized. This classification aims to provide a more up-to-date understanding of the SDPL. It is divided into two main classes: aqueous and evaporative deficiency. The category of aqueous deficiency refers mainly to a lack of tear secretion. The evaporative class has been subdivided to distinguish from causes that depend on intrinsic conditions of the eyelids and ocular surface and those that arise from extrinsic influences.

The SDPL can start in either of the two classes, but these are not mutually exclusive. It is recognized that a disease can start in a main class and coexist or even lead to events that produce SDPL by a mechanism of another kind. This is part of a vicious cycle of interactions that can amplify the severity. An example of this may be that all forms of SDPL cause loss of goblet cells, which over time will contribute to a loss of tear film stability, surface damage and evaporative water loss. [4]

Many pathophysiological mechanisms of the SDPL stimulate the sensory nerves of the cornea, so the SDPL is described as a "symptomatic disease". [13] [14] [15] In most patients there is a relationship between symptoms and clinical signs, nevertheless it is also recognized that in some patients the severity of the symptoms does not correspond to the clinical signs of the disease. [16] [14] [17]

The classification of the SDPL according to its severity currently represents a challenge, since there is no gold standard to determine it; notwithstanding, the severity of the disease is one of the most relevant factors when considering the therapeutic options for the SDPL. [18] In 2006 a panel of specialists, called the Delphi Panel, issued a classification of severity later adopted by the DEWS. The severity was classified into four levels, based on the increase in frequency and intensity of various signs and symptoms. [18] See **¡Error! No se encuentra el origen de la referencia.** 

There are other systems to classify the SDPL severity referred by other authors, [19] [20] [21] [22] among them the algorithm of the European consensus of the ODISSEY group which was designed to classify as severe patients with discordant SDPL and therefore, more complex to classify. [23]

In addition to the evaluation parameters of the SDPL, among which a greater correlation has been found, OSDI, TRL, and Schirmer's test, cytology by conjunctive impression (CIC) has been used recently, which is a minimally invasive technique that allows the analysis of the disease in a clinical setting by evaluating mainly the characteristics of goblet cells. CIC can be used for diagnostic purposes, to understand the mechanism of the disease and to evaluate the effectiveness of a treatment. [24]

# Primary Sjögren Syndrome Secundary Lacrimal Deficiency Obstruction of the lacrimal gland duct No sjögren syndrome Reflex blockage Systemic medications SDPL Meibomian deficiency Alterations of the opening of the eyelid Intrinsic Low index of blinking Action of medicines (Accutane) Deficiency of vitamin A Preservatives of topical medications Extrinsic Use of contact lenses Diseases of the ocular

**CONFIDENTIAL** 

surface ex. allergies

Grade	1 Mild	2 Moderate	3 Severate	4* Incapacitator
Discomfort, severity and frequency	Occurs mildly and / or episodically; under conditions of environmental stress	Occurs chronically or episodically, with or without environmental stress	Occurs frequently and / or constantly without stress	Is constant
Visual symptoms	None or episodic mild fatigue	Disturbances, activity limitation in an episodic manner	Disturbances, activity limitations in a chronic and / or constant way	Constant and / or disabling
Conjunctival injection	None to mild	None to mild	+	+/++
Conjunctival stain	None to mild	Variable	Moderate to marked	Marked
Corneal staining	None to mild	Variable	Central marking	Severe and disseminated dot erosion
Lacrimal / corneal signs	None	Mild debris, meniscus diminution	Filamentous keratitis, lacrimal debris and mucinous accumulations	Filamentous keratitis, lacrimal debris, mucinous accumulations, ulcer
Meibomian glands / eyelids	Meibomitis present in a variable way	Meibomitis present in a variable way	Frequent	Trichiasis, keratinization, simblefaron
TRL	Variable	≤ 10	≤ 5	Immediate
Schirmer I	Variable	≤ 10	≤ 5	≤ 2
* It must have sign	ns and symptoms.			

#### Table 2. Classification of the SDPL by severity

Adapted from Behrens A, Doyle JJ, Stern L, et al.[18]

The treatment currently available for the SDPL can be divided into:

- a) Lacrimal supplements: lubricants.
- b) Tears retention: lacrimal dot occlusion, contact lenses.
- c) Secretion stimulation: secretagogues.
- d) Biological substitutes: autologous serum, autologous salivary gland.
- e) Anti-inflammatories: cyclosporine, steroids, tetracyclines.
- f) Essential fatty acids
- g) Environmental strategies

The treatment recommendations of the American Academy of Ophthalmology and the Guidelines for the Dry Eye of the International Working Group, favored by the DEWS, are based on severity See ¡Error! No se encuentra el origen de la referencia.. The recommendations can be modified by the ophthalmologist, based on the clinical experience and the individual profile of your patient. [18] [25] [26]

#### Table 3. Treatment recommendations for the SDPL

Level 1:
Education and dietary and environmental modifications
Elimination of systemic medications that alter the UFL
Lubricants
Eyelid treatment
Level 2:
If the treatments of level 1 are insufficient, add:
Anti-inflammatories
Tetracyclines
Closing the puncta with silicone tips
Secretagogues
Level 3:
If the treatments of level 2 are insufficient, add:
Autologous serum
Contact lenses
Permanent closure of the lacrimal dots
Level 4:
If level 3 treatments are insufficient, add:
Systemic anti-inflammatories
Surgery (tarsorraphy, transplantation: mucous membrane, salivary gland,
amniotic membrane)
Modified from the Guidelines for the Dry Eye of the International Working Group [18]

The main objective in the care of patients with SDPL is to improve the patient's ocular comfort and quality of life, in addition to returning the ocular surface and the tear film to its state of homeostasis. Although the symptoms are rarely eliminated, they can often be diminished, resulting in an improvement in the quality of life. [26]

Ocular lubricants are the first line of management for the SDPL and a constant in all levels of treatment. They are characterized by hypotonic or isotonic solutions, which contain electrolytes, surfactants and various types of viscous agents. The main variables in the formulations of ocular lubricants are in relation to the selection or concentration of electrolytes, the osmolarity, the type of visco-polymeric system, the presence or absence of preservatives. [26]

# 5.2 Definition of the problem and fundamental reason

There are few effective treatments for the treatment of SDPL. The clinical development of new treatments is slow because the pathogenesis of SDPL is multiple and its semiotics variable. The different phases of treatment have as a common denominator the use of ocular lubricants.

Although there is a great variety of topical lubricants, with different viscous agents, there is no evidence that one is better than another. The elimination of preservatives, mainly benzalkonium chloride (BAK, for its acronym in English benzalkonium chloride) or the development of new less toxic preservatives have made eye lubricants more tolerable.

Although ocular lubricants have not been shown to be sufficient to completely resolve the alteration of the ocular surface and the inflammation seen in patients with SDPL, they have been shown to provide protection to the ocular surface and to diminish the symptomatology and clinical findings.

The combination of sodium hyaluronate (HS) and chondroitin sulfate (CS), which are biopolymers, glycosaminoglycans (GAG), constituents of the extracellular matrix, contributes to PRO-087 the viscoelastic and water retention properties, to function as a lubricant effective that protects the ocular surface and reconstitutes the tear film.

# 5.3 Background

In Mexico and other South American countries, Humylub Ofteno® is available, which is the association of HS and CS itself that contains PRO-087, but with BAK as conservative. Humylub Ofteno® has been registered in Mexico since July 2007 and there have been no reports of adverse reactions associated with the use of Humylub Ofteno®, maintaining a good safety profile. [27]

#### 5.3.1 Sodium hyaluronate

It is a biopolymer, disaccharide of the GAG family, formed by the alternating sequence of N-acetyl-D-glucosamine and glucuronate in linear chains. In physiological solvents it forms spirals; configuration determined by its viscosity. It is a constituent of the extracellular matrix, connective tissue, vitreous humor, umbilical cord, synovial fluid, skin, etc. It can be constituted by more than 10,000 pairs of disaccharides. At concentrations above 0.1% sodium hyaluronate constitutes a network. The diffusion rate through the network is inversely related to the size of the polysaccharide molecules, which are stable. Proteoglycans contribute to mechanical and elastic properties. Numerous authors have reported that the HS has a high capacity to retain water, it has been established that 1 gr of HS can retain up to 6L of water. [28]

Sodium hyaluronate is synthesized on the inner side of the plasma membrane as a linear polymer, in contrast to other GAGs which are synthesized by enzymes in the Golgi apparatus. The enzymes for the synthesis of sodium hyaluronate are hyaluronate and glucosyltranferases, which coordinately polymerize and translocate sodium hyaluronate out of the cell into the extracellular matrix. [29]

#### 5.3.1.1 Eyeball pharmacokinetics

Route of administration: Ophthalmic.

Release: immediate.

Absorption: HS absorption through the cornea has not been reported when applied to the ocular surface. Pharmacokinetic studies performed in patients with dry eyes showed that the HS solution reached its maximum concentration in 10 minutes and is widely distributed on the ocular surface.

Metabolism: it is biotransformed by hyaluronidases.

Elimination: it is eliminated from this compartment through the lacrimal sac and the lacrimal duct without intraocular absorption, in approximately 45 minutes. [30] Based on the results of preclinical research in rabbits developed by Laboratorios Sophia SA de CV, the ocular half-life correlates with the volume of the formula.

#### 5.3.2 Chondroitin sulfate

It is part of the group of GAGs, like sodium hyaluronate, is a mucopolysaccharide found in the extracellular matrix of connective tissues, including the vitreous, cornea and aqueous humor. GAGs are high molecular weight aggregates called proteoglycans. These proteoglycans contribute to provide mechanical and elastic properties to products containing CS. The CS monomer is a

disaccharide compound of N-Acetylgalactosamine and N-glucuronic acid. The sulfate group is fixed in galactosamine, in position 4 and 6, which explains the existence of 2 isomers of CS. [31]

#### 5.3.2.1 Eyeball pharmacokinetics

Route of administration: ophthalmic.

Release: immediate.

Distribution: on the ocular surface and nasal epithelium through the nasolacrimal duct. Absorption: from the formulation administered topically, it has been determined that there is no absorption through the cornea.

Metabolism: by phase I biotransformation reactions, oxidation and reduction. Elimination: through the tear system.

# 5.3.3 Use of conservators

The preservatives are used in order to inhibit microbial growth and suppress biodegradation inside medicines. [32] A great variety of conservatives have been used throughout history. The chronic use of drugs has been linked to irritation and alterations of the ocular surface, it has been established that the conservatives themselves have adverse events, which are attached to those of the active principle that preserve. [33]

The preservatives are classified into detergents and oxidants, and a more recent version of oxidants called buffered by ions. [32] The BAK is the most historically used preservative, belongs to the class of detergents. The reasons for its popularity include its broad spectrum of action and its familiarity with the formulator industry.

Although its effectiveness is well recognized, there are numerous studies documenting the harmful effects of BAK. BAK at concentrations of 0.05-0.1% induces necrosis and concentrations of 0.01% apoptosis. Its effects are cumulative and become more severe at higher concentration and with more frequent exposures. [32] [34] [35] It has been postulated that the presence of BAK is responsible for changes in the conjunctival surface identified by cytology by impression, such as the decrease in the density of goblet cells. [36] [37]

# 5.4 Justification

Patients who attend SDPL independently of its etiology and degree of severity will have to use ocular lubricants to reduce symptoms and improve their quality of life.

Ocular lubricants are the first line of drugs for eye symptoms related to tear film dysfunction in healthy subjects, with a prevalence of 25 to 35% in people over 60 years of age and 6% in those over 40 years. If we add to this those who mention occasional symptoms or who depend on a work or occupational situation and who use it for intermittent periods throughout their lives, the spectrum of population that will have access to these medications is very extensive. It is estimated that 50% of patients diagnosed with lacrimal film dysfunction without concomitant diseases will use more than 2 ophthalmic solutions in 5 years of treatment.

Taking into account the observation of the cumulative effect of conservatives such as BAK and that their adverse events are directly linked to the amount instilled and their repetitions, it is imperative to provide options that do not have aggravating inflammation secondary to the use of conservatives. Sophia Laboratories, S.A. of C.V.

PRO-087 is a preservative-free formulation that requires the documentation of your safety profile.

# 5.5 Objectives and hypothesis

# 5.5.1 General Objective

To evaluate the safety and tolerability of the preservative-free ophthalmic solution PRO-087 on the ocular surface.

### 5.5.2 Specific Objectives

- Describe the safety of the preservative-free ophthalmic solution PRO-087 by means of the density of goblet cells
- Describe the safety of the preservative-free ophthalmic solution PRO-087 by means of changes in intraocular pressure.
- Describe the safety of the preservative-free ophthalmic solution PRO-087 by means of changes in ocular surface stains.
- Describe the safety of the preservative-free ophthalmic solution PRO-087 through changes in laboratory tests.
- Describe the safety of the preservative-free ophthalmic solution PRO-087 by means of changes in vital signs.
- Describe the safety of the preservative-free ophthalmic solution PRO-087 by means of changes in visual capacity.
- Describe the safety of the preservative-free ophthalmic solution PRO-087 by means of changes in the tear-rupture time.
- Describe the safety of the preservative-free ophthalmic solution PRO-087 by means of changes in the ocular comfort index.
- Describe the safety of the preservative-free ophthalmic solution PRO-087 by means of changes in the posterior segment.
- Describe the safety of the preservative-free ophthalmic solution PRO-087 by means of changes in ophthalmological signs and symptoms.
- Describe the safety of the preservative-free ophthalmic solution PRO-087 when assessing the integrity of the anterior segment by means of fluorescein staining.
- Describe the safety of the preservative-free ophthalmic solution PRO-087 when evaluating the integrity of the anterior segment by means of the green lysine stain.
- Describe the safety of the preservative-free ophthalmic solution PRO-087 through the presentation of adverse events.

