#### 6.4 Outcome variables.

#### 6.4.1 Security variables.

#### 6.4.1.1 Primary outcome variables.

- Density of goblet cells
- Presence of adverse events.
- Intraocular pressure.
- Visual ability
- Laboratory tests: BHc, QS and PFH.
- Epithelial defects in cornea and conjunctiva.
- Ophthalmological signs: conjunctival hyperemia, chemosis.

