#### 6.4.3.6 Intraocular pressure.

Tonometry is the objective measure of IOP, based primarily on the force required to flatten the cornea or the degree of corneal indentation produced by a fixed force. Goldman's tonometry is based on the Imbert-Fick principle. [38] The tonometry will be performed, after instillation of a drop of topical anesthetic (tetracaine 0.5%), with fluorescein and the use of the cobalt blue filter (after evaluation of the corneal surface staining). There will be 3 shots, which will be recorded in the clinical file and the average will be registered in the CRF.

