#### 6.4.3.8 Vital signs.

The vital signs to be evaluated (FC, FR and TAS) can be measured by an assistant duly indicated in the organization of the center and the delegation of responsibilities, the technique to be used for the FC and FR will be with the count of repetitions in one minute by Direct auscultation with stethoscope.

The SBP should be measured with 5 minutes of previous rest, in the left arm. The instrument can be manual or automatic according to the IP. It is necessary that all measurements are equal in circumstances. 3 measurements will be made, with a minimum interval of 5 minutes between them. The IP will record the average in the note and the CRF.

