# Final Visit / Day 11.

It can be done in a period  $\pm 1$  day in relation to the 11th day of the start of application.

- 1. Visual ability
- 2. Density of goblet cells (Cytology per impression)
- 3. Intraocular pressure.
- 4. Eye comfort index
- 5. Evaluation of ocular signs and symptoms
- 6. Integrity of ocular surfacea. Includes stainsb. TRL
- 7. Subsequent segment evaluation.
- 8. Vital signs
- 9. Evaluation of adverse events.

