# 6.5 6.5 Timeline and study diagram.

Procedures	Scrutiny	Basal Visit	Visit 1	Visit 2	Final Visit	Call Security
i loccuares		Day 0	Day 3 ± 1	Day 6 ± 1	Day 11 ± 1	Day 13 ± 1
CI Signature	Х					
Clinic history	Х					
Ophthalmological clinical history	Х					
Laboratory sample taking	Х				Х	
Laboratory tests review		Х				х
Pregnancy test	Х				Х	
Eligibility criteria	Х	Xa				
Assignment		Х				
Delivery of intervention		Х	Х	Х		
Return of intervention			Х	Х	Х	
Adherence evaluation			Х	Х	Х	
Adverse events			Х	Х	Х	Х
Intraocular pressure	Х	X1	Х	Х	Х	
Visual ability	Х	X1	Х	Х	Х	
TRL	Х	X1	Х	Х	Х	
Epithelial defects (TF and TVL)	Х	X1	Х	Х	Х	
Eye signs and symptoms	Х	X1	Х	Х	Х	
posterior segment	Х	X1			Х	
Vital signs	Х	X1	Х	Х	Х	
Ocular Comfort Index		Х			Х	
Goblet cell density (cytology by impression)		х			х	
Daily delivery of the subject		Х	Х	Х		
Return / Evaluation of the subject's Journal			Х	Х	х	
Delivery Quality Questionnaire		Х				
Return and Evaluation of the quality questionnaire					Х	
Continuity evaluation of the subject			Х	Х		

a The eligibility criteria will be completed with the revision of the laboratory exams. 1 These measurements may be taken from the result of the screening visit, if it does not exceed the previous 7 days. It is the prerogative of the PI to decide whether to repeat the measurements at the baseline visit.

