#### 6.6.1 Calculation of the sample size.

Although there are no references on the calculation of sample size in phase I studies, it was considered pertinent to perform it according to the presentation of adverse events reported by Hwang HS, et al, in a case-control study in 150 subjects with ophthalmic solutions with Hyaluronate sodium and diquafosol with and without preservative for 3 months. [46].

The percentage of adverse events that occurred with the preservative-free HS solution was 8%, which is why we consider that at least more than 60% of the exposed subjects will not present this rate of adverse events.

The sample size was calculated using the formula for proportions

$$n = \left[ (p1)(p2) + (p1)(p2) \left( \frac{Z_{1-\alpha}}{2} + Z_{1-\beta} \right)^2 \right] / (p1 - p2)^2$$

With a statistical confidence of 95% corresponding to the type I error, equal to 1.96, with a power of 80%, corresponding to the type II error, equal 0.84.

According to the previous calculation, the result is 7.6 subjects (8) per group. The total when considering 3 intervention groups is 24 subjects, which was increased by 25% due to the probable losses. The total sample size required is 30 subjects. Therefore, each group will consist of 10 subjects, who will provide both eyes for the analysis, so that the total sample to be analyzed will be composed of 60 eyes.

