#### : www.randomization.com

3 strata corresponding to the intervention groups will be used, which will be balanced for a research center. The allocation will be 1: 1: 1.

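### The hour of tonometry is neither set, matched nor recorded, so any time-of-day variation adds avoidable noise to a primary safety variable in arms of 10

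*Combined protocol and SAP*

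**What the plan says.** Section 6.4.1.1 lists "Intraocular pressure" among the primary safety variables, and section 5.5.2 sets the objective in terms of its change: "Describe the safety of the preservative-free ophthalmic solution PRO-087 by means of changes in intraocular pressure".

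- **Technique.** Section 6.4.3.6 specifies Goldmann tonometry with a named anaesthetic, fluorescein and the cobalt blue filter, after the corneal staining has been assessed. On replication it says: "There will be 3 shots, which will be recorded in the clinical file and the average will be registered in the CRF". It does not mention the time of day.
- **Visits.** Section 6.4.4 schedules pressure at Day 0, Visits 1 and 2 and the Final visit. Each visit after baseline has a window in days. For the Final visit it is plus or minus one "day in relation to the 11th day of the start of application".
- **Baseline.** The footnote to the table in section 6.5 lets the Day 0 values, pressure included, come from screening: "These measurements may be taken from the result of the screening visit, if it does not exceed the previous 7 days". Whether to repeat them is the investigator's choice.
- **Conditions elsewhere.** For blood pressure, section 6.4.3.8 asks for rest, a fixed arm and spaced readings, and adds: "It is necessary that all measurements are equal in circumstances". Section 6.4.3.6 has no such sentence.
- **Size and analysis.** Section 6.6.1 states that "each group will consist of 10 subjects, who will provide both eyes for the analysis". Section 8.3.1 gives Wilcoxon tests within groups and Kruskal-Wallis between groups for continuous variables, with no covariates. It treats the product as safe and tolerable if no primary variable differs clinically and statistically from the comparators.

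**The concern.** A change in pressure compares readings taken on different days. If pressure varies with the hour, and a subject is seen early at one visit and late at another, the difference between the two hours enters that subject's change score. The protocol has no provision that limits this and none that would let an analyst see it afterwards.

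The two forms of replication in the plan do not help. The three readings are taken at one sitting and the second eye is measured at the same visit, so all of them carry the same time-of-day component.

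Extra spread makes a real pressure effect harder to detect. Under the decision rule in section 8.3.1, a missed effect counts towards a finding of safety, so the noise works in favour of the conclusion that the study hopes to reach.

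**Working it through.** **The plan's own figure.** There is none for pressure. Section 6.6.1 derives the sample size from adverse-event proportions: 8 per group, 3 × 8 = 24, 24 × 1.25 = 30, hence 10 per group. No standard deviation, effect size or margin for pressure is stated, so nothing can be reproduced for this variable.

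**Step 1: what averaging removes.** Write s_e for the error SD of a single reading and s_t for the time-of-day SD. The variance of a three-reading mean is s_t² + s_e²/3. With assumed s_e = 1.0 and s_t = 1.5 mmHg, the visit SD falls from √(1.5² + 1.0²) = 1.80 for one reading to √(1.5² + 1.0²/3) = 1.61 for the mean of three. However many readings are taken, it cannot fall below 1.5.

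**Step 2: inputs for the change score.** All three SDs are assumptions in mmHg, shown as ranges:
- e, error of the three-reading mean: 1 to 1.5
- y, day-to-day variation within a subject at the same hour: 1 to 1.5
- c, variation due to unmatched clock time: 1 to 2 (0 if perfectly matched)

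From the plan: 10 subjects per arm, alpha 0.05 (two-sided) and 80% power, the last two as used in section 6.6.1. The subject is the unit, because both eyes share the hour.

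**Step 3: formulas.**
- SD of change = √[2(e² + y² + c²)]
- Detectable difference = 1.325 × SD of change, where 1.325 is the standardised difference that a two-sample t test with 10 per arm detects with 80% power. This approximates a pairwise comparison. The planned test is Kruskal-Wallis.
- Variance ratio, unmatched to matched = (e² + y² + c²)/(e² + y²)

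**Step 4: results.**

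| e | y | c | SD of change | Detectable difference (mmHg) | Variance ratio |
|---|---|---|---|---|---|
| 1 | 1 | 0 | √4 = 2.000 | 2.650 | 1 |
| 1 | 1 | 1 | √6 = 2.449 | 3.246 | 3/2 = 1.50 |
| 1 | 1 | 2 | √12 = 3.464 | 4.590 | 6/2 = 3.00 |
| 1.5 | 1.5 | 0 | √9 = 3.000 | 3.975 | 1 |
| 1.5 | 1.5 | 1 | √11 = 3.317 | 4.395 | 5.5/4.5 = 1.22 |
| 1.5 | 1.5 | 2 | √17 = 4.123 | 5.463 | 8.5/4.5 = 1.89 |

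The detectable difference is about 2.7 to 4.0 mmHg at a matched hour and about 3.2 to 5.5 mmHg unmatched. The variance ratio, which is also the multiplier on sample size for equal precision, runs from about 1.2 to 3.

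**Step 5: if visit values are compared instead of changes.** Clock variance then enters once and sits beside the between-subject variance b². The ratio becomes (b² + e² + y² + c²)/(b² + e² + y²), which is smaller than the ratio in step 3 for any b > 0.

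**The case against.** Several points on the other side are sound.

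- **Silence on the hour.** A reader might infer that visits are held at any hour of the day. The documents do not say so. They leave the clock time open, and section 6.1 places the study in ophthalmology offices. Sites may already book similar hours, in which case the loss is smaller.
- **An outside premise.** No section states that pressure varies with the hour, and every SD above is assumed. This stands, and it is why the result is a range.
- **A larger multiplier.** If reading error were the only variation left once the hour is fixed, the variance ratio would run from 3.25/2.25 = 1.44 to 5/1 = 5.0, and a reader might conclude that up to five times as many subjects are needed. That is not supportable: the visits are days apart, so day-to-day variation at the same hour also remains.
- **Bias between arms.** A reader might fear that the hour favours one product. Section 7.1 states "The allocation will be 1: 1: 1", allocation is random, and subject and investigator are masked, so no between-arm bias is expected. Within-arm Wilcoxon comparisons lack that protection and could shift if baseline and later visits differed systematically in hour.
- **The blood-pressure contrast.** The sentence in section 6.4.3.8 sets no clock time either, and section 6.4.3.6 does standardise technique. The contrast shows only that the plan values comparable conditions. It does not show that the plan controls the hour for other variables.
- **Exploratory purpose.** Sections 5.5.2 and 5.6 describe an exploratory phase I study with descriptive objectives, and no power is claimed for pressure. Matching the hour also leaves the decision rule in section 8.3.1 as it is.

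These points limit the size and weight of the finding. None of them supplies a provision that sets, matches or records the hour.

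**Conclusion.** The point holds as a minor, inexpensive improvement in measurement. The protocol leaves the hour of tonometry uncontrolled and does not ask for it to be recorded, and neither triplicate readings nor the second eye can remove the resulting variation. The effect is added noise in a primary safety variable with 10 subjects per arm, under a rule that reads no difference as safe.

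The variance ratio of about 1.2 to 3 rests on the assumed SDs and on an analysis of change. Section 8.3.1 does not say whether the between-group test uses changes or visit values. The figures are an upper bound on the gain: a 2-hour window leaves some clock variation, sites that already book similar hours lose less, and a comparison of visit values is affected less.

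**What to change.** In sections 6.4.3.6 and 6.4.4, require each subject's pressure at Visits 1, 2 and Final to be measured within 2 hours of the clock time of the reading used as baseline. If a screening value is reused as baseline under section 6.5, its clock time sets the window. Record the time of every pressure measurement in the CRF, so that departures can be seen and, if needed, examined in the analysis.

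The cost is one CRF field and less flexible appointments. Visit days, procedures and sample size stay as they are.
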